1.5.2 Sample size for full trial (Stage 2)

If the trial is recommended to continue at Stage 2 based on DMC interim review, the full trial will need to recruit an additional 95 for each arm that continues (152 per arm in total; 456 to the complete trial). This will provide 90% power to detect a change of RR of 0.6 (50% to 30%), with one-sided alpha of 0.027 (chosen to give a 5% FWER) and has been inflated by 5% for missing outcome data. Here the power is the chance of an effective treatment passing stage 1 and being recommended after stage 2.

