3.2.5 Continuous laboratory values

For inflammatory markers of CRP, LDH, ferritin, D-dimer and serum creatinine levels a linear mixed effect model will be used to estimate the mean difference in values between intervention arms (RUX and FOS) and SOC at each follow-up visit (day 1, day 7 and day 14). Participants will be included as a random intercept with fixed effects for time, time-by-treatment arm interaction and baseline values. Stratification variables age and site, plus receipt of known effective treatments dexamethasone and/or tociluzimab, prior vaccination against COVID-19, and receipt of paxlovid and/or molnupiravir at the time of or prior to randomisation into MATIS will also be included as fixed effects. Baseline adjusted treatment group differences with 95% confidence intervals will be presented for each time-point.

For example for CRP the model to be fitted to estimate the treatment effect at each visit up to day 14 will be:

$$\begin{split} Y_{ijt} = \ \beta_0 + \ \beta_1 R U X_{ij} + \ \beta_2 F O S_{ij} + \ \beta_3 C R P_{ij}^0 + \ \beta_4 A G E_{ij}^0 + \ \beta_5 D E X_{ij}^0 \\ + \ \beta_6 T O C_{ij}^0 + \ \beta_7 V A C_{ij}^0 + \ \beta_8 P A X_{ij}^0 + \ \beta_9 M O L_{ij}^0 \ \beta_{10} time_7 \\ + \ \beta_{11} time_{14} + \ \beta_{12} R U X_{ij} * time_7 + \ \beta_{13} R U X_{ij} * time_{14} \\ + \ \beta_{14} F O S_{ij} * time_7 + \ \beta_{15} F O S_{ij} * time_{14} + \ \beta_{16} S I T E_1 \\ + \ \beta_{17} S I T E_2 + \dots + \ \beta_{18} S I T E_{j-1} + b_{1,i} + e_{it} \end{split}$$

for

t = 1 to 3 time points (day 1, 7 and 14), i = 1 to 30 participants

 RUX_{ij} : dummy variable for treatment ($RUX_{ij} = 0 \text{ or } 1$) for participant i

 FOX_{ij} : dummy variable for treatment ($FOS_{ij} = 0 \text{ or } 1$) for participant i

 CRP_{ij}^{0} : baseline CRP value for participant i

 DEX_{ij}^0 : dummy variable for receipt of dexamethasone at the time of or prior to randomisation (includes day of randomisation or one day post randomisation) ($DEX_{ij} = 0 \text{ or } 1$) for participant i TOC_{ij}^0 : dummy variable for receipt of tociluzimab at the time of or prior to randomisation (includes day of randomisation or one day post randomisation) ($TOC_{ij} = 0 \text{ or } 1$) for participant i VAC_{ij}^0 : dummy variable for prior vaccination against COVID-19 at the time of or prior to randomisation (includes day of randomisation or one day post randomisation) ($VAC_{ij} = 0 \text{ or } 1$) for participant i

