 PAX_{ij}^0 : dummy variable for receipt of paxlovid at the time of or prior to randomisation (includes day of randomisation or one day post randomisation) ($PAX_{ij} = 0$ or 1) for participant i

 MOL_{ij}^0 : dummy variable for receipt of molnupiravir at the time of or prior to randomisation (includes day of randomisation or one day post randomisation) ($MOL_{ij} = 0$ or 1) for participant i $time_x$: dummy variable for time (= 0 or 1) at time point x days. Day 1 is represented by $time_7 = 0$ and $time_{14} = 0$

Site_i: dummy variable for each of the jth sites

$$b_{1,i} \sim N(0, \sigma_{b1}^2), e_{it} \sim N(0, \sigma_e^2)$$

Where $b_{1,i}$ is the random intercept at the participant level. Each of $b_{1,i}$ and e_{it} are assumed to follow normal distributions. An unstructured covariance matrix will be used and the model will be fitted using restricted maximum likelihood (REML). This model makes assumptions about random effects distributions, correlation structures and residuals, which will all be investigated. If the model fails to converge model estimates will not be presented.

The above will be repeated for each inflammatory marker up to day 14 and additionally up to day 28.

References

- 2. Siddiqui O. Statistical methods to analyze adverse events data of randomized clinical trials. *Journal of Biopharmaceutical Statistics* 2009; 19: 889-899. DOI: http://dx.doi.org/10.1080/10543400903105463.
- 4. White IR, Royston P and Wood AM. Multiple imputation using chained equations: Issues and guidance for practice. *Statistics in Medicine* 2011; 30: 377-399. DOI: https://doi.org/10.1002/sim.4067.
- 5. Kahan BC. Accounting for centre-effects in multicentre trials with a binary outcome when, why, and how? *BMC Medical Research Methodology* 2014; 14: 20. DOI: 10.1186/1471-2288-14-20.
- 6. Kahan BC and Morris TP. Improper analysis of trials randomised using stratified blocks or minimisation. *Stat Med* 2012; 31: 328-340. 2011/12/06. DOI: 10.1002/sim.4431.

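### SAP 3.2.5 fits one baseline slope across all visits but reports a treatment difference at each visit; if the slope varies by visit, the day 14 and day 28 laboratory contrasts lose precision

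*SAP*

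**What the plan says.** SAP 3.2.5 sets as its target the "mean difference in values between intervention arms (RUX and FOS) and SOC at each follow-up visit (day 1, day 7 and day 14"). The model is described as follows: "Participants will be included as a random intercept with fixed effects for time, time-by-treatment arm interaction and baseline values". The worked equation for CRP agrees with the text. The baseline term, defined as the "baseline CRP value for participant i", appears once, with one coefficient, and the only products with the visit indicators are those for RUX and FOS.

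Reporting is by visit: "Baseline adjusted treatment group differences with 95% confidence intervals will be presented for each time-point". The model is then extended: "The above will be repeated for each inflammatory marker up to day 14 and additionally up to day 28". SAP 1.1.3 and 3.2 name days 14 and 28 as the times of interest for these outcomes.

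On the covariance, the SAP states: "An unstructured covariance matrix will be used and the model will be fitted using restricted maximum likelihood (REML"). The equation beside that sentence has one random intercept and one residual variance shared by all visits. On checking, it says: "This model makes assumptions about random effects distributions, correlation structures and residuals, which will all be investigated". No check of, or fallback for, the baseline slope by visit is named.

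**The concern.** A model that lets the treatment effect vary by visit but holds the baseline slope constant uses a compromise slope at every visit. Where the slope at a visit differs from the compromise, the baseline adjustment there is too strong or too weak, and the part that does not fit adds baseline noise to the treatment contrast.

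There is reason to think slopes could differ here. Patients enter during acute illness with a CRP of at least 30 mg/L at some time point (SAP 1.3.1). Follow-up runs from day 1 to day 28, and the blood tests after discharge are meant to track recovery (footnote to Table 1, SAP 1.2). A baseline value may say a good deal about the next day and little about two or four weeks later. At stake is the width of the intervals for five secondary laboratory outcomes at the visits the SAP singles out.

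**Working it through.** **Inputs from the documents.** Model terms, visit-specific target and covariance statement: SAP 3.2.5. Final sample size: "152 per arm in total; 456 to the complete trial" (SAP 1.5.2). The plan states no SD, correlation, precision or power for any laboratory outcome, so there is no figure to reproduce.

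**Inputs that are assumptions.** Correlations `rho_t` between baseline and days 1/7/14, and visit SDs relative to a baseline SD of 1. Two SD patterns were used: equal at all visits, and falling to 0.95/0.65/0.40.

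**Formula, random-intercept equation, complete data.** The raw slope at visit t is `g_t = rho_t × SD_t / SD_baseline`, and the fitted common slope is the average `g_mean`. The day 14 estimate is the difference in day 14 means minus `g_mean` times the difference in baseline means. Relative to a model with a slope per visit, the variance ratio is

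`1 + (g_14 − g_mean)² × SD_baseline² / [SD_14² × (1 − rho_14²)]`

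This is never below 1, and it equals 1 only when `g_14 = g_mean`. It does not depend on the sample size.

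**Worked case, 0.8/0.4/0.2.**

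- Equal SDs: slopes 0.8, 0.4, 0.2; mean 0.467. Ratio = 1 + 0.267²/0.96 = 1.074, so the SE is inflated by 3.6%.
- Falling SDs: slopes 0.76, 0.26, 0.08; mean 0.367. Ratio = 1 + 0.287²/(0.16 × 0.96) = 1.535, so the SE is inflated by 24%.
- Against no baseline adjustment at all, the common-slope variance at day 14 is `(SD_14² + g_mean² − 2 × g_mean × g_14) / SD_14²`. This is 1.03 with equal SDs and 1.47 with falling SDs, so in these two cases the common slope does worse than leaving baseline out.

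**Range.** Inflation of the true day 14 SE, complete data:

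| Correlations at days 1/7/14 | Equal SDs | SDs 0.95/0.65/0.40 |
|---|---|---|
| 0.5/0.5/0.5 | 0% | 7% |
| 0.6/0.5/0.4 | 0.6% | 13% |
| 0.7/0.5/0.3 | 2.2% | 20% |
| 0.8/0.4/0.2 | 3.6% | 24% |
| 0.9/0.3/0.1 | 5.5% | 29% |

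What drives the loss is the raw slope, not the correlation alone. Correlations of 0.8/0.4/0.2 with SDs of 1/2/4 give a slope of 0.8 at every visit and no loss.

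**Unstructured reading.** Here the common slope is a weighted average rather than a simple one. Taking residual correlation 0.5 between adjacent visits and 0.25 between days 1 and 14 (assumed), the large-sample inflation at 0.8/0.4/0.2 is 11% with equal SDs and 10% with falling SDs. At 0.7/0.5/0.3 it is 4% and 3%. At the most extreme setting, 0.9/0.3/0.1, it is 26% and 44%.

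**Simulation.** REML random-intercept fits, 152 per arm, 1,500 runs, the same residual correlations, at 0.8/0.4/0.2:

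| Data | True SE inflation, equal SDs | True SE inflation, falling SDs |
|---|---|---|
| Complete | 3.1% | 26.6% |
| 5/20/40% of visits missing at random | 8.4% | 36.7% |

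The missingness rates are assumed; the Table 1 footnote says only that visits after discharge are not mandated. Bias was about zero throughout. When slopes and SDs were in fact equal (0.5/0.5/0.5), the extra terms cost about 0.1% of the SE.

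**The case against.** The best case for the SAP is that a single baseline slope is a conventional specification, that these are secondary outcomes analysed only at the end with no power claimed, and that nothing in the documents shows the slopes to differ. All of that stands. It limits the point to an efficiency improvement and makes it conditional.

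A reader might go further and infer that baseline CRP is known to predict day 1 far better than day 14, so that a large loss is certain. The documents do not support this. They give no correlation, slope or SD for any marker, and SAP 1.9 describes the earlier CRP analysis without them. Nor does a falling correlation suffice: with equal SDs and the written equation it costs at most 5.5% over the range above. Large figures need the additional assumption that the spread shrinks. For example, correlations 0.85/0.40/0.15 with SDs 0.9/0.5/0.35 give a day 14 variance ratio of 1.69, like losing 1 − 1/1.69 = 41% of patients. That is an extreme setting under the random-intercept reading only, and should not be quoted as the expected loss.

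A reader might also infer that chance baseline imbalance biases the day 14 estimate. It does not. Under randomisation that shift is the same extra variance seen in a single sample.

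Finally, the intervals the model reports would narrow less than the true SE. At 0.8/0.4/0.2 the reported SEs differ by 4 to 6% with equal SDs and 14 to 18% with falling SDs. This is correct and belongs to the separate covariance problem noted under the fix.

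**Conclusion.** The point holds as a conditional one about precision. SAP 3.2.5 imposes one baseline slope on contrasts that it reports visit by visit, gives no reason for doing so, and plans no check of it. If raw slopes differ, the day 14 and day 28 contrasts are less precise than they need be.

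Under the equation as written with complete data, the inflation of the true day 14 SE is about 0 to 5.5% with equal SDs and 7 to 29% if the SD falls to 40% of baseline. Under the unstructured reading it is about 10 to 11% at 0.8/0.4/0.2, and more at steeper decay. Missing post-discharge visits could enlarge it; equal raw slopes remove it. Every one of these figures rests on assumed correlations and SDs. Day 28 was not computed separately, though the same algebra applies, and nothing shows that the other four markers behave as assumed for CRP. The primary outcome is untouched.

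**What to change.** In SAP 3.2.5, add the baseline value by visit interaction to the list of fixed effects and to the equation: `CRP0 × time_7` and `CRP0 × time_14`, plus `CRP0 × time_28` in the day 28 version, with the matching terms for each of the other markers. This costs two parameters per model, or three with day 28, against up to 456 participants, and one line of text and code. It should be settled before laboratory data are seen by arm.

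This change does not by itself resolve the conflict in the same section between a single residual variance in the equation and the stated unstructured covariance. In the complete-data simulations at 0.8/0.4/0.2 with one common variance, 95% intervals at day 14 covered about 90% of the time with equal SDs and 98 to 99% with falling SDs, with or without the interaction. The SAP should also say which covariance is meant and write the equation to match.
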